suggesting: a) strong initial uptake of e-cigarette, b) favorable liking/satisfaction/withdrawal relief, and c) that these effects are not nicotine specific (few differences between active vs. placebo). We also just completed a R21 that is thematically very similar to the current trial: 68 participants randomized to receive e-cigarettes (again, BluCig) or not, with a naturalistic sampling period and prospective follow-up. The R21 used ecological momentary assessment (EMA) methods to capture uptake patterns among smokers who are provided an e-cigarette. The study included a control group (Total N=68) that allows us to compare prospective changes in smoking behavior as compared to smokers who do not receive an e-cigarette (BluCig). Manuscript is in preparation and results are to be presented at SRNT 2017. Figure 1 shows uptake and amount of usage of e-cigarettes, during and following the sampling period. General uptake during the 3-wk sampling period was strong: 100% of those receiving BluCig used at least once, 71% reported regular use during at least 1 of the 3 sampling weeks, and 63% used daily during at least 1 week. Smokers in the e-cigarette group were 2.9x more likely (41 vs. 14%) to independently purchase their own e-cigarette, 1.6x more likely (44% vs. 27%) to make a quit attempt, and 3x more likely (15% vs. 5%) to achieve “floating abstinence” (any 7-day period of non-smoking, ever within study). Cessation-related outcomes were non-significant for this small study, and we caution against over-interpretation since confidence intervals (not shown here) are wide. We found significant reductions in both CPD and CO/NNAL, but no changes in cotinine. EMA data suggested clear contextual differences for e- vs. conventional cigarettes. EMA compliance was strong: 80% of participants completed at least 12 diaries in 3 weeks (most comparable to herein) and 78% completed at least 3 diaries/week. These early results show: a) general congruence of outcomes to those we hypothesize for the proposed larger trial, b) palatability of product, c) uptake/use even without structured instructions to do so, and d) our strong experience in methods: recruitment, sampling product, EMA, biomarkers, and product evaluation. The general methods and measures from these studies guide our current trial, though we now turn to a 2nd generation device, which should have even fewer barriers to uptake and/or substitution.

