Our study is not purely naturalistic, but it comes close. We provide product for free, mailed directly to participants. This allows us to examine uptake in the absence of cost/access barriers. Asking smokers to pay for e-cigarettes might provide a truly real world test of uptake, but without large numbers of participants, does not allow for assessment of uptake and impact on smoking. We have very little interaction with participants other than through assessments, and never instruct on cigarette or e-cigarette use. We provide referrals to cessation support (quitlines) for those who wish it. This is not a cessation trial, but rather an observational study of smokers over time, some of whom are randomized to receive e-cigarettes to use however they wish, or not at all. Randomization removes self-selection bias that is so common in the existing literature. It also allows for prospective analysis of uptake, use, trial, and adoption among smokers exposed/offered a product, with needed comparison to those who are not given product. Smokers both wanting to quit and not will be enrolled. Our primary focus in this study is the impact of e-cigarette use upon smoking behavior, with emphasis on uptake/usage/adoption, as well changes in smoking. However, with such a large study, among the first of its kind in the U.S., we believe that omission of cessation/quit attempt outcomes in this study would be a significant lost opportunity. Furthermore, if there are group differences in cessation, we believe it would be another lost opportunity to be underpowered to detect them. Thus, our trial is powered on naturalistic rates of point prevalence

abstinence at six-month follow-up, but we again emphasize that we are not promoting or testing e-cigarettes as a cessation intervention.

Regulatory Issues

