Control Group Smokers in this group will smoke their own brand of cigarettes, as they wish, for the duration of the sampling period, but will engage in all study assessments including diary assessments. We considered a placebo-controlled study, but our interest is not in the pharmacological intake of nicotine (vs. not), but rather the use (inclusive of behavioral substitution) vs. non-use of e-cigarettes. Blinding of active vs. placebo e-cigarettes is easily managed for lab-studies, but less so for nationwide, naturalistic studies. To control for cost differential with e-cigarette group, participants in the control group will receive extra reimbursement; we do not want changes in behavior to be a function of free product. We debated whether to provide same general message of e-cigarettes as above. On one hand, doing so would decrease study-induced demand to try e-cigarettes, making this equivalent across groups. However, this would artificially inflate e-cigarette use within the non-sampling control group, which impinges on internal validity. We opt not to include such messaging, but will acknowledge

this as a potential confound. We do anticipate that some control participants will use e-cigarettes, and this too is an outcome we assess (along with all other uptake variables). Within our R21, 1/21 control participants (4.7%) used an e-cigarette (see Figure above). E-cig use is escalating, but still low and we expect nominal initiation within control group. Primary analyses will be based on ITT principles (i.e., group assignment as the independent variable, not product use).

Smokers in both groups will be assessed at screening for interest in cessation support. All comers will be accepted, but smokers actively using cessation medication at baseline will be excluded. At all contacts, we will assess motivation to quit and, as necessary, offer referral information to state quitlines. Such transitions to cessation support are included as study outcomes.

Diary of E-cigarette Uptake

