All analyses are based on an intent-to-treat approach, and are nearly identical to analyses from our prior studies. Exploratory analysis will be performed on all outcomes, and both graphical displays and summary statistics will help determine if transformations will be needed. Any significant baseline differences between groups will be included in regression analyses described below. Missing Data: The most conservative approach for handling missing data (136) is to substitute them with baseline values, assuming outcomes have all returned to baseline, with no quit attempts made. If this assumption is incorrect, it biases the results towards the null by reducing between group differences (136). SRNT recommendations (136) suggest that when there are small amounts of missing data (< 10%) the conservative approach can be used with little bias in outcome. If missing data >10%, we will calculate results not only using this conservative method but also using methods in which missing data are imputed as described in the SRNT guidelines. We will also assess whether dropout is differential by study group. In our current and recent studies of cessation induction, this has not been the case, and we expect similar results here. Finally, though sex/gender is not an explicit focus, we are well poised, given our sample size, to address **potential sex/gender influences** on study outcomes.

Hyp 1a: Within the e-cigarette group, we hypothesize that at least 90% of smokers will try at least once, 45% will use regularly (at least 4/7 days, at any time during follow-up), 25% will use daily for ≥ 7 days (at any time during follow-up), 25%/10% will be using at least some/daily at final follow-up, and 20% will independently purchase e-cigarettes. Within the e-cigarette group (N=440), we will analyze prevalence of each definition of uptake. We will estimate each of these parameters, and the 95% confidence interval for each proportion.

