This fully detailed section is based on the recommendations in NCI's "Guidelines for Developing a Data and Safety Monitoring Plan" as well as NIDA's "Guidelines for Developing a Data and Safety Monitoring Plan."

1. Summary of the Protocol

Eligible smokers, once consented (process described below), will be randomized to receive a onetime sample of e-cigarettes (NJoy; n=440) or not (n=220). E-cigarette samples are inclusive of a battery and self-contained tanks of assorted flavors to last up to 4 weeks. Participants will be recruited nationally, but a subset (N=120) will be recruited locally to allow for biomarker collection (locally recruited participants will be managed via phone/mail as are all other participants; details below). All smokers will be asked to provide smoking diary data, captured electronically, daily for 4 weeks. More substantive phone assessment will track smoking and related behaviors at baseline (Day 0) and +10, +17, and +24 days (weekly during initial 3 weeks, following brief lag for delays in product mailing), and at +1, +3, and +6 months (7 phone assessments total). Major outcomes during both the sampling and follow-up periods are noted below.

2. Primary and secondary outcomes

During the sampling period and beyond, uptake of e-cigarettes is the primary outcome. Uptake is defined in several ways, including a) first time use, b) repeat use, c) first time buyer, d) repeat buyer, and e) advocacy; i.e., promoting/suggesting to others. Following a brief sampling period, smokers are then followed for six months, in which outcomes include subsequent e-cigarette use, biomarkers of exposure, quit attempts, and cessation.

3. Inclusion/exclusion criteria

General Inclusion / exclusion criteria are as follows:

- a) age 21+,
- b) current smoker of ≥ 5 cigarettes per day for ≥ 1 year,
- c) no recent history of cardiovascular distress (heart attack in past 3 months; arrhythmia, uncontrolled hypertension), or renal disease (e.g., dialysis) that would interfere with urinary biomarker assessment
- d) neither pregnant nor breastfeeding,
- e) at least some concern for health effects of smoking (>none at all on a Likert scale),
- f) no current use of cessation medication,
- g) have not purchased in the past 6 months or ever regularly used (daily or weekly) a tank system, mechanical mod, or advanced personal vaporizer e-cigarettes
- h) no regular use (daily or weekly) of any e-cigarette (including cig-a-like devices) in the last 6 months,

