Minorities are also included in this study, at proportions (aggregate 22%) generalizable to US Census data, wherein 78% of US residents are White, 13% Black, 5% Asian, 1% Native American, and <1% native Hawaiian or Pacific Islander. These same census data indicate that 17% of the US residents are of Hispanic origin. The Targeted Enrollment Table reflects these proportions accordingly. We have chosen recruitment cities that meet or exceed national estimates proportions of minorities and/or Hispanics, which should facilitate recruitment goals.

8. Data Acquisition and Transmission

Participants are recruited nationally, and contacted via mail and phone. The study will be managed centrally from the Division of Clinical Neuroscience within the Department of Psychiatry and Behavioral Sciences at the Medical University of South Carolina (MUSC), but physically based within the Cancer Control Program of the Hollings Cancer Center, where the PI is based. A subset of study visits will occur in lab space within our study group. Urine assays will be managed locally within our departmental lab.

9. Data Analysis Plan

Data will be entered centrally by research assistants directly in real time, into a computer-assisted telephone REDCap (Research Electronic Data Capture) database. RedCAP is a secure, web-based application designed exclusively to support data capture for research studies. Our group has been using REDCap for all studies since 2009, reducing errors with data entry. All databases are password protected. Cotinine and carbon monoxide data will be managed through the Department of Psychiatry's Clinical Neurobiology Lab. Samples will be stored in deidentified fashion, with unique SID numbers alone.

Hyp 1a: Within the e-cigarette group, we hypothesize that at least 90% of smokers will try at least once, 45% will use regularly (at least 4/7 days, at any time during follow-up), 25% will use daily for ≥ 7 days (at any time during follow-up), 25%/10% will be using at least some/daily at final follow-up, and 20% will independently purchase e-cigarettes. Within the e-cigarette group (N=440), we will analyze prevalence of each definition of uptake. Each of these outcomes will be estimated, and 95% confidence intervals will be calculated for each.

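### Uptake, the stated primary outcome, is planned only as e-cigarette-arm proportions, so as written the plan cannot separate purchase or later use due to sampling from background uptake

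*Combined protocol and SAP*

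**What the plan says.** Section 2 of the Data and Safety Monitoring Plan (Primary and secondary outcomes) states: "During the sampling period and beyond, uptake of e-cigarettes is the primary outcome". It lists first and repeat use, first and repeat purchase, and recommending the product to others.

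The analysis of uptake is given twice. Under Hyp 1a in Statistical Considerations – Data Analyses: "Within the e-cigarette group (N=440), we will analyze prevalence of each definition of uptake". Section 9 of the Data and Safety Monitoring Plan repeats this and adds: "Each of these outcomes will be estimated, and 95% confidence intervals will be calculated for each". The Sample Size & Power section says that the primary outcome concerns the e-cigarette group alone and gives this as the reason for 2:1 allocation. The Aim 1 precision paragraph is likewise worked out for 440 e-cigarette participants only.

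Three other places point toward a comparison:

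- The section asking whether the trial is naturalistic, observational but randomised says that randomisation permits prospective analysis of uptake and adoption "with needed comparison to those who are not given product".
- The Control Group section says of e-cigarette use by controls that "this too is an outcome we assess (along with all other uptake variables", and that controls complete every study assessment, diaries included.
- The same section says that primary analyses follow intention-to-treat, with assigned group as the independent variable.

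No between-arm contrast for uptake appears under Hyp 1a, 1b, 2 or 3 or in the ancillary analyses. The nearest item is a secondary look at the stability of e-cigarette and cigarette use over time, with no group contrast stated. Contrasts by group are written out for cigarette reduction, biomarkers, quit attempts, abstinence and motivation.

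**The concern.** A single-arm proportion has no group variable. For the outcome called primary, the plan therefore does not carry out the comparison that its design section promises or that its own rule for primary analyses implies.

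This matters for outcomes that controls can also have. First use of the supplied product has a natural within-arm meaning. Independent purchase (20% expected) and use at final follow-up (25% any, 10% daily) can also occur in smokers who are sent nothing. The Control Group section expects only nominal initiation among controls, but it also says that e-cigarette use is escalating, and recruitment is to last 42 months. The pilot did report purchase by arm: the e-cigarette group was "2.9x more likely (41 vs. 14%) to independently purchase their own e-cigarette". Background purchase was therefore not zero there.

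If only the e-cigarette-arm proportion is reported, the same 20% is compatible with a large effect of sampling or a small one. Any statement about adoption due to sampling would then rest on an unplanned comparison or on none.

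**Working it through.** **Inputs from the documents.** Arms of 440 and 220; two-sided alpha 0.05; expected e-cigarette-arm rates of 20% (purchase), 25% (any use at final follow-up) and 10% (daily use at final follow-up); pilot purchase 41% vs 14%. No control-arm uptake rate is given for this trial, so the control rates below are assumptions shown as a range.

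**The plan's own figure.** The half-width for one proportion is 1.96 × √(p(1−p)/440). At p = 0.50 it is 0.0467, giving 0.453 to 0.547. At p = 0.90 it is 0.028, giving 0.872 to 0.928. Both match the Aim 1 precision paragraph, so its arithmetic is correct. At p = 0.20 the half-width is 0.0374, so the planned purchase result would read 20% (16.3% to 23.7%).

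**The missing contrast, purchase.** The difference is p1 − p0, with half-width 1.96 × √(p1(1−p1)/440 + p0(1−p0)/220). For p0 = 0.14: √(0.16/440 + 0.1204/220) = 0.0302, × 1.96 = 0.059. For p0 = 0.05: √(0.16/440 + 0.0475/220) = 0.0241, × 1.96 = 0.047. The 7% row keeps the pilot's ratio: 41/14 = 2.93 and 20/2.93 = 6.8%, rounded to 7%.

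| Assumed control purchase | Difference, points (95% CI) | Background share of the 20% | Power |
|---|---|---|---|
| 5% | 15.0 (10.3 to 19.7) | 25% | >99% |
| 7% (pilot ratio) | 13.0 (8.0 to 18.0) | 35% | >99% |
| 10% | 10.0 (4.6 to 15.4) | 50% | 92% |
| 14% (pilot control rate) | 6.0 (0.1 to 11.9) | 70% | 47% |

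Power is for a two-sided comparison of two proportions without continuity correction. It reaches 80% for purchase when the control rate is at most about 11.5%.

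**Use at 6 months, same formula.** Any use, 25% in the e-cigarette arm: control 5% gives 20.0 points (15.0 to 25.0), 10% gives 15.0 (9.3 to 20.7), and 15% gives 10.0 (3.8 to 16.2). Daily use, 10% in the e-cigarette arm: control 2% gives 8.0 points (4.6 to 11.4), and 5% gives 5.0 (1.0 to 9.0).

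**Precision.** The largest half-width for a difference is 1.96 × √(0.25/440 + 0.25/220) = 0.081, against 0.047 for the single-arm rate. With 400 and 200 (the 600 participants before the attrition allowance) it is 0.085.

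**The pilot's control figures.** The Control Group section gives "1/21 control participants (4.7%) used an e-cigarette", while the account of the same pilot gives 14% purchasing. The pilot account also gives control rates of 27% and 5% for other outcomes. With 21 controls, 27% cannot occur (5/21 = 24%, 6/21 = 29%). With 22, all three fit (3/22 = 14%, 6/22 = 27%, 1/22 = 5%). The two statements may therefore use different denominators, and possibly different time windows. The first refers to a figure that the available text does not show.

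**The case against.** The strongest reply is that the single-arm analysis is intended and coherent. Aim 1 is worded as description, the sample-size section ties the primary outcome and the 2:1 allocation to the e-cigarette arm, and the Regulatory Issues section puts the main focus on patterns of use during sampling. Hyp 1a makes no causal claim, and nothing in the documents says that reaching 20% purchase will be credited to sampling. All of this stands. It is why the within-arm estimates should stay. It does not remove the mismatch with the section that justifies randomisation or with the group-assignment rule.

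Four stronger readings are tempting, and the documents do not support them.

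- *The trial cannot answer the question, or the control data will go unused.* The limit lies in the analysis as written. Controls complete all assessments, their uptake is named as an assessed outcome, and exploratory analysis of all outcomes is planned.
- *Most of the 20% purchase would be background.* This needs the trial's expected 20%, which is below the pilot's 41%, to be paired with the pilot's unreduced 14%. That control rate comes from a very small group: if it is 3/22, the exact 95% CI is about 3% to 35%. Keeping the pilot's ratio gives a background share of about a third.
- *Use at 3 or 6 months is independent of study product.* The E-cigarette Group section says that product is not returned and that participants keep what remains after sampling. Later use can therefore be leftover supply.
- *The pilot's 1/21 and 14% contradict each other and show a high background rate.* They call for clarification. They do not establish a rate.

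A between-arm difference also reflects the message encouraging use, which only the e-cigarette arm receives. The Control Group section acknowledges this as a potential confound, and it applies to purchase as well as to later use.

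**Conclusion.** The point holds as a gap between the stated primary outcome, the stated reason for randomising and the written analysis. Under Hyp 1a as it stands, purchase and later use due to sampling cannot be told apart from background uptake.

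The size depends on a control rate that the documents do not give. At 20% purchase and full arms of 440 and 220, the difference runs from 15.0 points (10.3 to 19.7) at a control rate of 5% to 6.0 points (0.1 to 11.9) at 14%. These are Wald intervals with no missing data. The 20% is the plan's expectation and every control rate is an assumption.

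Purchase is the cleanest contrast because it does not include use of leftover study product. Differences in later use remain informative as the effect of being assigned to the sampling package.

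**What to change.** In Hyp 1a of Statistical Considerations – Data Analyses, and in its copy in section 9 of the Data and Safety Monitoring Plan:

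1. Keep all within-arm estimates as they are.
2. For independent purchase and repeat purchase, and for any and daily e-cigarette use at 3 and 6 months, add the control-arm proportion and the between-arm risk difference with its 95% CI, by randomised group.
3. Label these as planned estimates, and state that any claim about adoption due to sampling will rest on them.
4. Note that differences in later use include leftover study product, and that all the differences include the message given to one arm only.

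Reconcile the sample-size section's single-arm description of the primary outcome with the design section's promised comparison and the Control Group section's group-assignment rule. State the denominator and time window behind the pilot's 1/21 and 14%.

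The cost is analysis wording only, with no added data or participants. The difference is less precise than the single-arm rate (largest half-width 0.081 against 0.047, so wider than the ±5% accepted for Aim 1). Power for purchase is about 47% if controls purchase at 14%. The contrast should therefore be reported as an estimate with its interval and not judged on significance alone.

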Sample size estimate for local subset, to capture biomarkers of exposure We searched for prospective e-cigarette studies (controlled or not) that were NOT cessation based but reported on biomarkers, either CO or cotinine. We found only one (47) but acute decreases (within 1 month) in CO were only indirectly reported (in graph, separated by smoking group outcomes). Consistent with those data, we expect an overall decrease in CO within 1month of 35%, compared with no such decreases within the control group. A sample size of 80 in the e-cigarette local subset group (total of n=120 for the local subset who complete the baseline in-person lab visit) will have at least 80% power to detect a 35% decrease in CO (23.5ppm to 15.3ppm in the e-cigarette group vs. no change in the control group, assuming a standard deviation of 15.0 in the control group and 10.0 in the e-cigarette group (standard deviations were estimated from the interquartile ranges reported in the Polosa study (47) using standard procedures (134)). We expect no group differences in cotinine. We recognize that this technically implies a test of equivalence, and we are willing to accept up to +/-3% difference to conclude equivalence. With a local subset sample size of n=120 (40 control and 80 e-cigarette), $\alpha=0.05$, a two-sided t-test has >90% power to reject the null hypothesis that the two groups are not equivalent (1400ng/ml +/- 45ng/ml) in favor of the alternative hypothesis that the mean cotinine levels of the two groups are equivalent (assuming an expected difference in means of 0ng/ml and a common standard deviation of 70.0ng/ml) (135).

Statistical Considerations – Data Analyses

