Hyp1b: Among smokers in the e-cigarette group, 40% will show a minimum of 50% reduction in cigarettes per day, and as a group, e-cigarette users will show greater decreases in cigs/day as compared to control. Reduction of cigarettes per day will be calculated based on the TLFB at baseline and 6 months for both groups, with “reducers” defined as those that reduce cigarettes per day by $\geq 50\%$. We will estimate the mean reduction, 95% confidence interval on the reduction, and the proportion of those that are considered “reducers” in both groups, the latter tested via a chi-square test with $\alpha=0.05$ two-sided significance level.

Hyp2: Within a subset of locally recruited smokers, we hypothesize that use of e-cigarettes will lead to significant decreases in CO and NNAL, but no net change in overall nicotine exposure. Changes in CO, NNAL and cotinine will be calculated based on the baseline, 1, and 6-month measurements. Mean change in CO/NNAL (thru 1 and 6 months) will be compared via a two-sample t-test with $\alpha=0.05$ significant level. In order to test equivalence for change in cotinine between the two groups, the TOST procedure (137) will be followed where two one-sided tests will be used to test that the difference in the change between groups (Δ) is within the +/-3% bounds that we are willing to accept ($H_{01}: \Delta < -3\%$; $H_{02}: \Delta < +3\%$). If Δ is contained completely within the +/-3% bounds, then equivalence will be concluded. We will use an $\alpha=0.05$ significance level.

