Hyp1b: Among smokers in the e-cigarette group, 40% will show a minimum of 50% reduction in cigarettes per day, and as a group, e-cigarette users will show greater decreases in cigs/day as compared to control. Reduction of cigarettes per day will be calculated based on the TLFB at baseline and 6 months for both groups, with “reducers” defined as those that reduce cigarettes per day by $\geq 50\%$. We will estimate the reduction, 95% confidence interval on the reduction, and the percent of those that are considered “reducers” in both groups, the latter tested via a chi-square test with an $\alpha=0.05$ two-sided significance level.

Hyp2: Within a subset of locally recruited smokers, we hypothesize that use of e-cigarettes will lead to significant decreases in CO, but no net change in overall nicotine exposure. Changes in CO and cotinine will be calculated based on the baseline, 1, and 6-month measurements. Change in CO (thru 1 and 6 months) will be compared via a two-sample t-test with $\alpha=0.05$ significant level. In order to test equivalence for change in cotinine between the two groups, the TOST procedure (137) will be followed where two one-sided tests will be used to test that the difference in the change between groups (Δ) is within the $\pm 3\%$ bounds that we are willing to accept ($H_{01}: \Delta < -3\%$; $H_{02}: \Delta < +3\%$). If Δ is contained completely within the $\pm 3\%$ bounds, then equivalence will be concluded. We will use an $\alpha=0.05$ significance level.

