Hyp 3: Provision and use of e-cigarettes will lead to increased incidence of (Hyp3a) quit attempts, (Hyp 3b) cessation, and (Hyp 3c) motivation/confidence to quit. Logistic regression analyses will be performed with (1) any quit attempt within 6 months (1=one or more quit attempts, 0=none), (2) any 24hr quit attempt (1=one or more 24 hour quit attempt, 0=none), (3) point prevalence abstinence at 6 months (1=7 day abstinence at 6 month call, 0=not abstinent), and (4) floating abstinence (1=any 7 day period of abstinence during study, 0=no abstinence) as the outcomes and group (e-cigarette vs. control) as the covariate. The coefficient on group provides a log odds ratio for measuring the increased odds of (1) any self-defined quit attempts, (2) 24hr quit attempts, (3) point prevalence abstinence, and (4) floating abstinence in the e-cigarette group compared to the control group. Statistical significance of these coefficients will be assessed using a p-value with a two-sided alpha of 0.05, and both the odds ratio and its 95% confidence interval (CI) will be reported. Motivation and confidence to quit are evaluated on a continuous scale (0-10), and linear regression models will be used with motivation/confidence to quit at 6 months as the outcomes with group (e-cigarette vs. control) as the covariate (along with baseline motivation/confidence and any other variables that are different between groups at baseline treated as covariates). Secondary analyses will include regression analyses where number of quit attempts are compared across groups using poisson or linear regression (depending on the distribution of number of quit attempts). We will also repeat this analysis: a) based on those who do vs. do not use e-cigarettes, and b) using quit attempts and abstinence of all tobacco products, including e-cigarettes.

10. Quality Assurance Plan

The REDCap system has validation options to not accept outliers, illogical response patterns, etc. The PI will have weekly meetings with the research assistants to discuss qualitative comments received during data collection and any problems in data collection. The statistician will periodically examine the database to look for irregularities. Initial data analyses will examine distributions of variable scores, comparability of baseline characteristics, follow-up rates and use of extra-study cessation treatment across conditions in case analyses need to be adjusted for these.

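### Hyp 2 tests change in CO, NNAL and cotinine without adjusting for baseline, which gives up precision; whether the CO power survives depends on what the stated SDs describe

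*Combined protocol and SAP*

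**What the plan says.** In Statistical Considerations – Data Analyses, Hyp2, the biomarker outcomes are differences from baseline: "Changes in CO, NNAL and cotinine will be calculated based on the baseline, 1, and 6-month measurements". For CO and NNAL, "Mean change in CO/NNAL (thru 1 and 6 months) will be compared via a two-sample t-test". For cotinine, "In order to test equivalence for change in cotinine between the two groups, the TOST procedure (137) will be followed", with bounds of ±3%. The Data and Safety Monitoring Plan, section 9 (Data Analysis Plan), repeats this for CO and cotinine: "Change in CO (thru 1 and 6 months) will be compared via a two-sample t-test". No covariate is named for any of the three markers.

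The general covariate rule at the start of Data Analyses covers only variables that differ significantly between arms at baseline, and only regression models. The Hyp 2 tests are not regressions, so the rule does not reach them. By contrast, section 9 models motivation and confidence to quit "along with baseline motivation/confidence and any other variables that are different between groups at baseline treated as covariates".

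The sample-size paragraph for the local subset says that 80 e-cigarette participants (120 in total) "will have at least 80% power to detect a 35% decrease in CO". The fall is from 23.5 to 15.3 ppm against no change in controls, "assuming a standard deviation of 15.0 in the control group and 10.0 in the e-cigarette group". These SDs were derived from interquartile ranges in one published cohort. The paragraph does not say whether they describe CO at a visit or change between visits, and it gives no correlation between visits. For cotinine it powers equivalence of the two groups' mean levels, with a margin of ±45 ng/ml around 1400 and an SD of 70.

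**The concern.** A t-test on change fixes the coefficient on baseline at 1. When follow-up correlates imperfectly with baseline, that over-corrects and adds noise, and a regression that estimates the coefficient does better. The loss falls on the biomarker comparison, which as planned has 40 controls and 80 e-cigarette participants and carries the whole of Aim 2.

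The power paragraph may also describe a different analysis from the one planned. If its SDs are of level, the CO calculation compares follow-up levels, whereas Hyp 2 compares changes. For cotinine the mismatch is explicit: power is stated for equivalence of levels, and the test is of equivalence of change. In both cases the power of the planned test then depends on a correlation that the plan never states.

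**Working it through.** **Inputs.** From the local-subset sample-size paragraph: n = 40 control and 80 e-cigarette; CO difference 23.5 − 15.3 = 8.2 ppm; SDs 15.0 and 10.0; cotinine margin 45, SD 70, true difference 0. Alpha is 0.05, taken as two-sided for CO. Assumed: the correlation r, over a range.

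**Step 1: reproduce the plan's CO figure.** SE² = 15²/40 + 10²/80 = 5.625 + 1.25 = 6.875, so SE = 2.622 and 8.2/2.622 = 3.127. Power is Φ(3.127 − 1.960) = 87.8% by the normal approximation and 86.7% for a Welch t-test. With SD 15 in both arms it is 80.6%. The stated figure of at least 80% is met either way.

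**Step 2: precision, equal SDs at both visits within an arm.** The change-score variance is 2(1−r)·SD² and the baseline-adjusted variance is (1−r²)·SD². The ratio is (1−r²)/[2(1−r)] = (1+r)/2, which gives 0.65 at r = 0.3, 0.75 at 0.5 and 0.85 at 0.7. The ratio does not depend on the size of the SD.

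**Step 3: precision, shared baseline SD.** Step 2 applied to SDs of 15 and 10 would give randomised arms different baseline SDs. A more coherent version takes baseline SD 15 in both arms, follow-up SD 15 in controls and 10 in the e-cigarette arm.
- Change variances are 450(1−r) and 325 − 300r. At r = 0.3, SE² = 315/40 + 235/80 = 10.81.
- The common adjusted slope is b = r(40·225 + 80·150)/(120·225) = 0.778r. At r = 0.3, b = 0.233, the residual variances are 205.75 and 91.25, and SE² = 5.144 + 1.141 = 6.28.
- The ratio is 6.28/10.81 = 0.58. At r = 0.5 it is 0.67.

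**Step 4: CO power if 15.0 and 10.0 are SDs of level** (Welch, 40/80):

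| r | Change, same SD at both visits | Adjusted | Change, shared baseline SD 15 | Adjusted |
|---|---|---|---|---|
| 0 | 58.5% | 86.7% | 54.2% | 86.7% |
| 0.2 | 68.1% | 88.1% | 63.5% | 88.0% |
| 0.3 | 73.8% | 89.7% | 69.1% | 89.5% |
| 0.4 | 80.1% | 91.8% | 75.5% | 91.6% |
| 0.5 | 86.7% | 94.4% | 82.5% | 94.1% |
| 0.7 | 97.8% | 99.0% | 95.8% | 98.8% |

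Threshold for 80%: SE² must not exceed (8.2/2.802)² = 8.57.
- Same SD at both visits: 2(1−r)·6.875 = 8.57 gives r = 0.38 (0.40 with Welch).
- Shared baseline SD: 15.31 − 15r = 8.57 gives r = 0.45 (0.47 with Welch).

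**Step 5: CO power if they are SDs of change.** Step 1 applies as it stands, at about 87%.

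**Step 6: cotinine.** SE = 70·√(1/40 + 1/80) = 13.56. Power is 2Φ(45/13.56 − 1.645) − 1 = 90.6%, which reproduces the stated figure above 90% for levels. If 70 is the SD of level at both visits, the test on change (SD 70·√[2(1−r)]) has 75.4%, 83.4% and 90.6% at r = 0.3, 0.4 and 0.5. The adjusted analysis has 93.4%, 95.2% and 97.1%.

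**The case against.** The strongest reply is that nothing planned is invalid. A change-score comparison in a randomised trial uses the baseline and is unbiased. That stands: this is a point about efficiency.

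A reader might go further and infer that the CO comparison is underpowered or its power misstated. The documents do not support that. Failure needs two things they leave open: SDs of level, and r below about 0.40 to 0.47. The effect is worded as a decrease, which is compatible with SDs of change. The level reading is the more natural one: Sample Size & Power describes the source cohort as uncontrolled, so a control-group SD of change could not have been observed there. It remains an inference. Nothing in the documents suggests a low r, and at r = 0.5 the planned test keeps 82% to 87%.

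It would also be too strong to say that adjustment is never less precise. With 2:1 allocation and one common slope, the change score can win in large samples, but only if follow-up rises more than one-for-one with baseline within an arm. That is unlikely here but not excluded.

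Three smaller replies have some force.
- The plan does not say which t-test it means. A pooled test shows more power (91.7% in simulation at the stated SDs), but its simulated type I error there is about 8.5%, against 5.0% for Welch.
- From November 2021 all participants are asked for remote CO readings, so the CO sample might exceed 120; Hyp 2 and the sample-size paragraph still name the local subset.
- The precedent of adjusting motivation for its baseline appears in section 9 but is not spelled out in the parallel Hyp 3 text under Data Analyses.

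**Conclusion.** The point holds as one of efficiency, with a conditional remark on power. Hyp 2 leaves out a covariate that is already collected. With equal visit SDs the adjusted variance is 0.65 to 0.85 of the change-score variance for r from 0.3 to 0.7; at r = 0.5, a change-score analysis would need 120/0.75 = 160 people to match 120 analysed with adjustment. With a shared baseline SD of 15 the gain is larger. These sizes rest on assumed r.

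The CO power statement is arithmetically sound. It stands if the SDs are of change, and is at risk under the planned test only if they are of level and r is under about 0.40 to 0.47 with all 120 analysed. With an assumed 10% loss (36/72), that threshold becomes 0.46 to 0.52. Under the level reading, the adjusted analysis with all 120 keeps about 87% or more at any r from 0 up, so its power no longer hangs on the unstated correlation. For cotinine, the powered quantity (levels) and the tested quantity (change) need to be reconciled.

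**What to change.** - In Data Analyses, Hyp2, and in section 9 of the Data and Safety Monitoring Plan, make the analysis a linear regression of the 1-month and 6-month value on arm and the participant's own baseline value. Use heteroscedasticity-robust standard errors, because the plan assumes unequal SDs and allocates 2:1. With baseline in the model, the arm coefficient is the same whether the outcome is the follow-up value or the change, so the hypothesis about change is still answered.
- Take the cotinine 90% confidence interval from the same model and state the margin on that model's scale: either ±45 ng/ml, or ±3% expressed as a ratio on the log scale. The two are not identical, since 3% of 1400 is 42 ng/ml, so one should be chosen.
- In the local-subset sample-size paragraph, say whether 15.0 and 10.0 are SDs of level or of change. If of level, restate the power for the adjusted analysis.

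The cost is wording only. No new data, visits or participants are needed.
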